**Funding Source:**

This project has received preliminary approval from the Merck Investigators Studies Program (MISP) with a budget of \$72,146.78. The budget for the study includes cost of the drug (Sugammadex), pharmacy and IRB fees, and payment for the research team. We will provide the budget for the study along with the rest of the protocol.

**Study Summary:**

Postoperative urinary retention following laparoscopic inguinal hernia repair occurs in approximately one out of ten patients. The more rapid reversal of neuromuscular blockade with Sugammadex has empirically been associated with low rates of postoperative urinary retention. In this study, patients will receive Sugammadex following laparoscopic inguinal hernia repair and then be retrospectively matched against a group of patients who did not receive Sugammadex. The primary aim of this study will be to compare the rate of postoperative urinary retention between patients receiving Sugammadex and those receiving traditional reversal agents (e.g. neostigmine which has a retention rate of 5-11%). We will also examine difference in cost and quality of life between the two groups. Our hypothesis is that the use of Sugammadex will decrease rate of postoperative urinary retention, decrease associated cost, such as need for admission, and not negatively impact quality of life.

**Background and Rationale:**

Urinary retention is a common complication following laparoscopic inguinal hernia repair, with recent studies citing the rate of postoperative urinary retention anywhere from 5-11%. Age, history of benign prostatic hypertrophy, general anesthesia, male gender and postoperative narcotic use have been associated with urinary retention following laparoscopic inguinal hernia repair. The exact effects of general anesthesia and a systemic paralytic agent on bladder function and urinary retention are not completely clear. However, it is strongly suggested that the lack of complete bladder musculature recovery and function in the immediate postoperative period and may lead to urinary retention.

Our institutional database contains over 2,500 patients who have undergone either unilateral or bilateral laparoscopic inguinal hernia repair. Currently our overall rate of urinary retention in all patients in our database is 7.3%, or 185 of the 2,551 patients. In the 90 patients who were both over the age of 60 and had benign prostatic hypertrophy symptoms, the rate was 15.6%. Postoperative urinary retention potentially requires prolonged post-anesthesia care unit (PACU) stay, overnight hospital admission, return to the emergency department, need for an indwelling catheter and further physician assessment,

prolonged micturition difficulties, and urinary tract infection and other catheter-related complications.

Urinary retention can be detrimental to the overall health of our surgical patients.

Sugammadex has been anecdotally reported to decrease rates of postoperative urinary retention following laparoscopic inguinal hernia repair. The more rapid reversal of neuromuscular blockade helps to explain this claim. In other areas of surgery, such as orthopedics, Sugammadex has already been associated with reduced anticholinergic usage and decreased rates of postoperative urinary retention. The cost efficacy of Sugammadex has yet to be determined as it is more expensive than traditional reversal counterparts; however, if it significantly decreases rates of postoperative urinary retention it could reduce healthcare costs that are downstream. Given that the reported incidence of postoperative urinary retention is high after laparoscopic inguinal hernia repair, and given this is one of the most common general surgery operations performed, the results of this study will certainly be widely applicable.

### **Study Objectives**

#### *Objectives –*

1. The primary objective of this study will be to compare urinary retention rates when using Sugammadex for neuromuscular reversal compared to neostigmine. The patients receiving Sugammadex will be enrolled prospectively and those who received neostigmine will be identified retrospectively on chart review.
2. We will secondarily evaluate length of stay (in postoperative recovery or in the hospital), charges accrued by patients, and quality of life compared to patients who received neostigmine.

#### *Hypotheses –*

1. We hypothesize that the use of Sugammadex as a neuromuscular reversal agent will decrease postoperative urinary retention after laparoscopic inguinal hernia repair compared to patients who received neostigmine.
2. We also hypothesize that there will be decreased postoperative length of stay, total hospital charges accrued by patients, and no negative impact on quality of life compared to patients who received neostigmine.

**Study Design/Methods:**

In this study, a prospective cohort of patients undergoing laparoscopic inguinal hernia repair will receive Sugammadex and then retrospectively be matched against a cohort of patients who did not receive Sugammadex. The patients will be matched based on age, gender, history of BPH, bilateral vs. unilateral hernia, opioid usage with morphine milliequivalents, and operative time. The patients will be consented when they present to clinic for the evaluation of their inguinal hernia as the primary means of consent or in the preoperative area as a secondary means of consent. The operating surgeon will notify the research team, consisting of a resident physician and two full time research analysts, when the patient is in clinic and expresses interest in the study. One of the members of the research team will see the patient and consent them for the study as the primary consent process. Patients will be identified prior to the day of surgery and, if not previously contacted in clinic, will be contacted via telephone about participating in the study. If the patient agrees to participate prior to the day of surgery, a member of the aforementioned research team will consent the patient on the day of surgery prior to the procedure as the secondary consent process. Inclusion and exclusion criteria are defined below. Neither the patient nor the surgeon will be blinded in this study, but we do not anticipate that this will in any way change management.

*Inclusion Criteria:*

- Over the age of 18
- Undergoing laparoscopic inguinal hernia repair at Carolinas Medical Center by attending surgeons within the Division of Gastrointestinal and Minimally Invasive Surgery
- Unilateral or bilateral inguinal hernia repair; may have concurrent umbilical hernia repair performed
- Agreeable to participation in the study

*Exclusion Criteria:*

- Patients who are having concurrent ventral or flank hernias repaired at time of operation or are having an inguinal hernia repair along with another operation (e.g. laparoscopic cholecystectomy)

- End-stage renal disease (Creatinine clearance less than 30)
- Neuromuscular disease
- Prior adverse reactions to Sugammadex
- Patients who do not provide consent for the study

[figure not shown]
On the day of surgery, the research team will be present in the preoperative area and communicate directly with the anesthesia team that this is a patient who will be receiving Sugammadex; this communication is important because Sugammadex can only reverse vecuronium or rocuronium. The Investigational Drug Service Department at Atrium Health will be notified the day before that there will be a patient included in the study the day prior to the operation. Their pharmacists will have the drug present for the anesthesiology team. This will not be a blinded study, so the anesthesia team and even the surgeon can know that the patient is receiving Sugammadex. In this study, patients will receive Sugammadex, in accordance with FDA approved labeling, following laparoscopic inguinal hernia repair and then be retrospectively matched against a group of patients who did not receive Sugammadex.

The definition that we will be using for urinary retention is the inability to void at six hours postoperatively which will be recorded in the postoperative recovery area and the same definition for urinary retention will be applied to the comparative retrospective cohort. Patients will be required to void prior to their discharge from the hospital. The requirement for urinary catheterization will be secondarily recorded. The details of the patient's operation, postoperative recovery, and potential admission encounter will be obtained and enter into the electronic health record into our pre-existing hernia database. Details about the cost to the patient will be obtained from a monthly billing statement that is generated for our department in Epic™ Systems. Patients will be seen in clinic postoperatively, typically within one to two weeks, and a quality of life questionnaire will be administered. This questionnaire is the same form that is typically used in our surgical clinics and will provide a means for retrospective comparison.

The data entry will be performed by two data analysts that are employed by our division. Once this data has been entered for all patients, our statistician will perform an analysis using Statistical

Analysis Software, version 9.4 (SAS Institute, Inc., Cary, NC) and send this data to the investigators for review. The principal investigator (PI) and co-investigators will be responsible for composing the abstracts and manuscript for this project.

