**Statistical Analysis and Sample Size Justification:**

*Variables/Time Points of Interest* – Basic demographic information for each patient will be obtained from the medical record, such as age, gender, ASA class, and prior medical histories/surgeries. This information will aid in propensity matching for the study. The propensity match will be 1:1 with an equal number of patients in each group. The match will ensure that there is no statistical difference in data points between the groups and it will be performed by our statistician using SAS. The primary outcome variable, postoperative urinary retention, is a categorical variable (yes/no) that will be documented in postoperative recovery after the patient's operation. Length of stay and hospital cost, continuous variables, will be recorded at the completion of the patient's hospital stay. Information about quality of life will be obtained postoperatively in clinic. The demographic information, primary and secondary outcomes will be entered into our institutional database along with the other information that is typically recorded, such as operative characteristics and patient follow up.

*Statistical Methods* - Data will be analyzed using Statistical Analysis Software, version 9.4 (SAS Institute, Inc., Cary, NC); this task will be performed by the statistician employed by our division. Descriptive statistics will be reported as means with corresponding standard deviations for continuous variables and percentages for categorical variables. Continuous and ordinal variables will be evaluated with the Wilcoxon-Mann Whitney and the Kruskal-Wallis tests. The Wilcoxon-Mann Whitney test will be used when normality exists and there are two variables for comparison, otherwise, the Kruskal-Wallis test will be used. For categorical variables, a Pearson chi-square will be used, and a Fisher exact test will be utilized with a small sample size (i.e. less than five). A two-sided p-value of <0.05 will be used for all significance determinations.

*Power/Sample Size* – Using SAS, the power for our study was calculated using the postoperative urinary retention rate at our institution, 7%, compared to a current 0.5% postoperative urinary retention rate using Sugammadex. With 80% power, we would need to enroll 140 patients per group. The data for this project will be interpreted by the PI for the project as well as the co-investigators.

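### Does matching on opioid dose without a stated time window bias the retention comparison?

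*Combined protocol and SAP*

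**What the plan says.** Study Design/Methods describes a prospective Sugammadex cohort matched to patients identified retrospectively: "The patients will be matched based on age, gender, history of BPH, bilateral vs. unilateral hernia, opioid usage with morphine milliequivalents, and operative time". Opioid dose has neither a start nor an end time.

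Statistical Analysis and Sample Size Justification adds: "The propensity match will be 1:1 with an equal number of patients in each group". As examples of what feeds the match it names demographics, ASA class and medical or surgical history. It mentions neither opioids nor a time limit on covariates.

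The reversal agent is given after the repair. The primary outcome is "inability to void at six hours postoperatively which will be recorded in the postoperative recovery area". Background and Rationale, listing risk factors, says that "male gender and postoperative narcotic use have been associated with urinary retention following laparoscopic inguinal hernia repair". That is the only opioid exposure the plan links to retention.

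**The concern.** Opioid dose is the one matching variable that can go on accruing after the reversal agent is given, and even after the outcome is assessed. Because the Background names postoperative narcotic use, a reader could take the match to include recovery-room or whole-stay doses.

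A whole-stay total could then depend on the outcome. According to the Background, "Postoperative urinary retention potentially requires prolonged post-anesthesia care unit (PACU) stay, overnight hospital admission". Study Design/Methods adds: "Patients will be required to void prior to their discharge from the hospital". The Hypotheses section expects that with Sugammadex "there will be decreased postoperative length of stay". A longer stay leaves more time in which doses are counted. If retention raises the total, matching would drop some controls with retention, lower the control rate and understate the benefit. If doses also differ between the cohorts for other reasons, the error could go either way. If Sugammadex itself reduces opioid use, matching on that use would remove part of its effect. The primary comparison is at stake, in a study powered at only 80%.

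**Working it through.** **1. The plan's own figure.** Inputs from the Power/Sample Size paragraph: 7% versus 0.5%, 140 per group, two-sided 0.05. Exact power of Fisher's test is the sum over i and j of Bin(i; 140, 0.07) × Bin(j; 140, 0.005), taken over tables with p < 0.05. The result is 0.803, matching the stated 80%. The opioid question does not alter this figure.

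**2. If retention raises the counted dose.** Everything about opioids here is assumed, because the documents give no opioid data. Dose is N(0,1) without retention and N(d,1) with it. There are 140 treated patients and 2,400 controls (assumed; the database has 2,551 patients). A logistic propensity score uses dose and five unrelated covariates, with greedy 1:1 matching and 5,000 runs per row.

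| d (SD) | Matched control rate | Fall from 6.97% (points) | Fisher power |
|---|---|---|---|
| dose not matched | 6.97% | – | 0.796 |
| 0.5 | 6.89% | 0.08 | 0.791 |
| 1.0 | 6.55% | 0.42 | 0.753 |
| 1.5 | 6.17% | 0.80 | 0.694 |
| 2.0 | 5.53% | 1.44 | 0.594 |

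A smaller pool (500 controls) or a 0.2 SD caliper gives nearly the same rates. The error is toward no effect.

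**3. If the cohorts also differ in dose.** With 7% in both groups, d = 1 and a cohort difference of −0.3 or +0.3 SD, the matched control rate is 5.40% or 9.01%. With no cohort difference it is 7.01%. A 600-run repeat of the two shifted cases gave two-sided Fisher rejection of 3.8% and 5.0% (SE about 0.9 points). The estimate moves, but false positives do not clearly exceed 5%.

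**4. If the reversal agent changes later opioid use.** Assume that Sugammadex lowers dose by 0.5 unit. If dose then affects retention (log-odds 0.5 per unit) and is the only route of benefit, matching on it takes a true difference of −1.2 points to 0.0. With an unmeasured common cause of dose and retention as well, −1.6 becomes +0.9. If the reversal agent does not affect opioid use, there is no bias (0.0 stays 0.0; −4.9 stays −4.9).

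**5. The cost of leaving postoperative dose out.** Let the retention rate be the average over dose x of 1/(1 + exp(−(c + β(x + s)))), with x standard normal, s the cohort difference in dose, and c set so that the rate is 7.0% at s = 0.

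- With β = ln 1.5 and s = −0.3, the rate is 6.26%. The spurious difference is 7.00 − 6.26 = 0.74 points, against 0.08 to 0.42 points in step 2 at d = 0.5 to 1.
- The dose model in step 2 makes the log-odds of retention rise by d per unit of dose, since −(x − d)²/2 + x²/2 = dx − d²/2. So d = 1 corresponds to an odds ratio of e¹ = 2.7 per SD. With β = 1 and s = ∓0.3, the unmatched rates are 5.38% and 9.02%.

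Those last two figures are almost exactly those of step 3. If retention drives dose, matching creates the distortion. If dose drives retention, failing to match leaves it in place. The association alone cannot tell the two apart.

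**6. The text set side by side.** Age, gender, BPH history, laterality and operative time are all fixed by the end of surgery, and the statistics section's examples are all baseline items. An opioid dose counted up to reversal fits that list. The Background sentence is a review of risk factors and does not define the matching variable.

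**The case for a change.** The strongest case for a change is that the postoperative reading is natural. Postoperative narcotic use is the only opioid risk factor named, matching is done retrospectively, and details of recovery and any admission go into the database. A window chosen once outcomes are known is an undisclosed analytic choice. A study powered at 80.3% has no reserve, and one added sentence would be cheap.

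Part of this stands. The text is silent, and doses given after the six-hour assessment cannot have caused the outcome, so a whole-stay total would be a poor choice. But that argues against one way of filling the gap, and the plan does not adopt it. Restricting the primary match to doses before reversal is not clearly better. The controls are retrospective, opioid practice may have differed, and the restriction would leave unbalanced a factor that the plan associates with retention. A sensitivity match using doses up to six hours would still condition on post-treatment dose, and it needs dose times that the documents do not say are available. The large losses (power of 0.694 or 0.594) need retention to raise dose by 1.5 or 2 SD, for which the documents offer no support.

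**Conclusion.** No change to the plan follows. The missing window is an undefined term that the statistician has to settle to build the match, and the surrounding variables point to a sensible answer. If doses up to reversal are meant, the bias is nil. If later doses are counted, a rise of 0.5 to 1 SD due to retention costs 0.1 to 0.4 points in the control rate and takes power from about 80% to 79% or 75%, in the conservative direction. Larger or two-sided errors need further assumptions: a bigger rise, a cohort difference in dose, or an effect of the reversal agent on opioid use. Whether doses between reversal and six hours belong in the match is a judgement between conditioning on a post-treatment variable and leaving a named risk factor unbalanced. Either choice can be defended, and the documents give no data to rank them. All sizes beyond the reproduced 0.803 power rest on assumed opioid effects.

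### The operating surgeon is in neither matching list and the test is unadjusted, so a different surgeon mix in the two groups could bias the retention comparison by an unknown amount, in either direction

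*Combined protocol and SAP*

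**What the plan says.** The combined protocol and SAP bears on this in five places.

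- **Matching variables, Study Design/Methods:** "The patients will be matched based on age, gender, history of BPH, bilateral vs. unilateral hernia, opioid usage with morphine milliequivalents, and operative time".
- **Matching variables, Statistical Analysis and Sample Size Justification:** basic demographic information, "such as age, gender, ASA class, and prior medical histories/surgeries. This information will aid in propensity matching for the study". The match is 1:1, and the section says it will leave no statistical difference in data points between the groups.
- **Who operates:** the inclusion criteria require repair "by attending surgeons within the Division of Gastrointestinal and Minimally Invasive Surgery". The number of surgeons is not given.
- **How patients enter the Sugammadex group:** "The operating surgeon will notify the research team, consisting of a resident physician and two full time research analysts, when the patient is in clinic" (provided that interest in the study is shown). There is a second route: patients are identified before the day of surgery and, "if not previously contacted in clinic, will be contacted via telephone about participating in the study".
- **Where controls come from:** Study Objectives says neostigmine patients are found by retrospective chart review. No restriction by surgeon or calendar period is stated. Background and Rationale describes the institutional database: "Our institutional database contains over 2,500 patients who have undergone either unilateral or bilateral laparoscopic inguinal hernia repair".

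The primary comparison (Statistical Methods) is a Pearson chi-square test, or Fisher's exact test when counts are below five, two-sided at 0.05. No covariate adjustment is planned.

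**The concern.** A variable confounds this comparison if it is related both to group membership and to the outcome. Surgeon may well be both. It can affect membership because the surgeon triggers the primary consent route, and because the control group reflects whichever surgeons operated in an unspecified earlier period. It can affect outcome through operative technique, perioperative practice, and decisions on catheterisation and admission. Those decisions also act directly on length of stay and charges, the secondary outcomes.

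Matching on patient characteristics does not balance a variable left out of the match, and an unadjusted test does not correct it afterwards. If surgeons with low retention rates contribute more to the Sugammadex group than to the controls, part of their advantage is read as a drug effect. In the opposite case, part of a real benefit is hidden.

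**Working it through.** **The plan's own figure.** With 7% vs 0.5% and 140 per group, exact enumeration of the two-sided Fisher test gives 80.3% power, which matches the stated 80%. The concern does not alter the sample size.

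**How uneven can current enrolment be?** Study Duration gives five repairs a week and 40 weeks: 5 × 40 = 200 cases, of which 140 (70%) must enrol. Assume two surgeon groups with equal current volume, 100 cases each.

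- Ceiling: one group enrols all 100 and the other 40. Share = 100/140 = 71.4%.
- Moderate case: 85 and 55 enrol. Share = 85/140 = 61%.

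The ceiling is soft. The protocol calls five a week conservative, which would loosen it; the 40 weeks also include analysis time, which would tighten it.

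**Expected rates with no drug effect.** Assumed surgeon-group rates are 4% and 10%, and controls are split 50:50. With share *s* from the low-rate group, the expected rate is *s* × 4% + (1 − *s*) × 10%.

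- Controls: 0.5 × 4 + 0.5 × 10 = 7.0%, the plan's control rate.
- 61% share: 0.61 × 4 + 0.39 × 10 = 6.34%, a spurious reduction of 0.66 points.
- 71.4% share: 0.714 × 4 + 0.286 × 10 = 5.71%, a spurious reduction of 1.29 points.

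If the high-rate group is over-represented instead, the Sugammadex rates become 0.61 × 10 + 0.39 × 4 = 7.66% and 0.714 × 10 + 0.286 × 4 = 8.29%, so the bias hides a similar amount of benefit.

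**Chance of p < 0.05 with fewer Sugammadex events.** Sum the product of the two binomial(140) probabilities over all outcomes that reject in that direction:

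| Sugammadex vs control | Pearson chi-square | Fisher |
|---|---|---|
| 7.0% vs 7.0% (no imbalance) | 2.3% | 1.4% |
| 6.34% vs 7.0% (61% share) | 3.8% | 2.3% |
| 5.71% vs 7.0% (71.4% share) | 6.0% | 3.7% |

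Expected event counts are 140 × 0.0571 = 8.0 and 140 × 0.07 = 9.8, both above five, so chi-square is normally the planned test. Fisher applies when counts turn out small.

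**The case against.** The strongest reply has four parts.

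**Surgeon notification is not a gate.** A reader might infer from "The operating surgeon will notify the research team" that surgeons decide who enters the Sugammadex group. The documents do not support that: patients missed in clinic are telephoned. This weakens surgeon-driven selection. It does not equalise consent between surgeons, and it has no bearing on the surgeon mix of the historical controls.

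**Extreme shares are not supported.** A reader might suppose that 75% or 90% of Sugammadex patients come from the low-rate group, which at the same assumed rates would give 7.0% or 12.9% by chi-square. With current volume split equally, the protocol's own caseload caps the share near 71%. Larger shares need a different surgeon mix in the control period or an unequal current split, and the documents are silent on both. One might also infer that controls span about ten years (2,551/(5 × 52) = 9.8). That assumes constant volume at a rate the protocol calls conservative, and controls drawn from the whole database; neither is stated.

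**The inputs are assumed.** No surgeon-level rates are given, and the risk factors listed in Background and Rationale do not include surgeon. This stands, and it is why the figures only illustrate.

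**Surgeon may be partly covered.** Operative time and opioid use may carry some of the surgeon difference, and the statistical section's list is open-ended, so surgeon is unspecified rather than ruled out. That also stands in part. But surgeons with similar operative times can differ in other practices, and a matching variable chosen only at analysis gives no assurance in advance.

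**Conclusion.** The concern holds as a gap in confounding control: if the plan is followed as written, surgeon mix is left to chance and referral. The direction and size of any bias are unknown. Under the assumptions above (two surgeon groups, 4% and 10%, equal current volume, controls 50:50), it is about 0.7 to 1.3 points, and the favourable false-positive chance by chi-square rises from 2.3% to between 3.8% and 6.0%. A reader might infer that surgeon mix could by itself explain the planned effect. It would not: the planned difference is 7.0 − 0.5 = 6.5 points. The risk is that a smaller true effect is exaggerated or masked, and that length of stay and charges are affected too. The point is worth correcting because the remedy is cheap, but it does not invalidate the study.

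**What to change.** Before matching is run:

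1. In Study Design/Methods and in the statistical section, name the operating surgeon as a propensity covariate. Match exactly on surgeon only where balance on age and BPH history is kept.
2. Draw controls from the surgeons who enrol patients, where possible.
3. Tabulate surgeon by group in the baseline table.
4. Add a surgeon-stratified (Mantel-Haenszel) sensitivity analysis of retention.

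The cost is one routinely recorded operative variable and some protocol wording; no extra patients are needed. The downside is somewhat fewer close controls per patient and sparse strata for surgeons with few neostigmine cases. The database holds 2,551/140 = 18.2 patients per planned enrolment before restriction to eligible neostigmine cases, but the number available per surgeon is not given. That is why exact matching on surgeon should be conditional: forcing it could worsen balance on age and BPH, which the protocol does identify as risk factors.

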**Study Duration:**

Conservatively, the Division of Gastrointestinal and Minimally Invasive Surgery group performs five laparoscopic inguinal hernia repairs per week. A total of 140 patients will receive Sugammadex in the study. If all patients undergoing laparoscopic inguinal hernia repair agreed to participate in the study, then it would require 28 weeks for all patients to have surgery. Given that not all patients will not be agreeable to participation, and to allow time for statistical analysis, we estimate that 40 weeks will be required to complete the study.

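### The secondary charges comparison sets current Sugammadex bills against older neostigmine bills with no control years, calendar matching or common price year, so it is confounded by price year

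*Combined protocol and SAP*

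**What the plan says.** Study Objectives lists charges as a secondary outcome, and Hypotheses gives it a direction: "decreased postoperative length of stay, total hospital charges accrued by patients". The two groups come from different periods. Sugammadex patients are enrolled prospectively, while "those who received neostigmine will be identified retrospectively on chart review". No start or end date for the controls is given.

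Study Design/Methods names the source of the amounts: "Details about the cost to the patient will be obtained from a monthly billing statement". It also lists the matching variables: "The patients will be matched based on age, gender, history of BPH, bilateral vs. unilateral hernia, opioid usage with morphine milliequivalents, and operative time". Statistical Analysis and Sample Size Justification adds demographics, ASA class and prior history to the propensity match. Neither list contains date or year of surgery.

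The same section compares continuous variables by rank tests without covariates (Wilcoxon-Mann-Whitney or Kruskal-Wallis, which with two groups are in effect the same test), at two-sided 0.05. No section mentions a price year, an index or an adjustment for time.

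**The concern.** Matching on patient characteristics balances patients, not prices. Even a perfect 1:1 match on every listed variable would compare bills issued under different price lists. Any general change in charges between the two periods then enters the comparison as if it were an effect of the reversal agent.

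If charges rose, older control bills look cheaper. That can hide a real saving with Sugammadex, or give a significant excess where there is none. If charges fell, the sign reverses. Either way, a result for or against the charges hypothesis could not be attributed to the drug. This matters more because the saving expected from avoided retention is small on the scale that a rank test measures, as shown below.

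**Working it through.** **The plan's own figure.** The only stated sample size, 140 per group, is for retention (7% against 0.5%, 80% power, two-sided 0.05). It is reproduced by the exact power of Fisher's test: 79.9% at 139 per group and 80.3% at 140. No figure is given for charges, so there is none to reproduce.

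**Inputs from the documents:** 140 per group, two-sided 0.05, a rank test, and retention of 7% and 0.5%.

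**Assumed inputs (not in the documents):** annual price growth g, lag L in years between control and Sugammadex bills, coefficient of variation CV of bills, and log-normal bills with no true difference at current prices.

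**Step 1, price gap.** A control bill lies 1 − 1/(1+g)^L below current prices.
- 1 year: 2.9% (g = 3%) to 6.5% (g = 7%).
- 3 years: 8.5% to 18.4%.

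**Step 2, shift on the rank scale.** With s = √ln(1+CV²), the lag lowers the probability that a control bill exceeds a Sugammadex bill by Φ(L·ln(1+g)/(s√2)) − 0.5. At CV 0.4, s = 0.385.
- 2%, 1 year: 0.0145.
- 3%, 1 year: 0.0216.
- 7%, 1 year: 0.0494.
- 3%, 3 years: 0.0646.
- 7%, 3 years: 0.1453.

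**Step 3, chance of p<0.05 with no true difference.** The null standard error of that probability is √((2n+1)/(12n²)) = √(281/235,200) = 0.0346. For 3% and 1 year, 0.0216/0.0346 = 0.63, so the chance is Φ(0.63 − 1.96) + Φ(−0.63 − 1.96) ≈ 10%. The other shifts above give about 7%, 30%, 46% and 99%. Simulation of the test (4,000 trials per cell, 140 per group) agrees. Each range below runs from 3% to 7% growth a year:

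| CV | 1-year lag | 3-year lag |
|---|---|---|
| 0.2 | 23-79% | 96-100% |
| 0.4 | 10-31% | 47-99% |
| 0.6 | 7-17% | 26-84% |
| 1.0 | 6-10% | 14-52% |

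With no lag the simulated rate is 5%. At 2% a year and a 1-year lag it is about 5-7% for CV 0.4 to 1.0. With zero growth there is no bias; with falling charges the sign reverses.

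**Step 4, scale against the effect sought.** Suppose that avoided retention is the only effect and that every retained patient's bill exceeds every other bill. At the plan's rates, the probability that a control bill exceeds a Sugammadex bill is then 0.07×0.995 + 0.5×0.07×0.005 + 0.5×0.93×0.995 = 0.5325, against 0.500 under no effect. That gain of 0.0325 is the most that avoided retention can give. A 1-year lag at 3-7% and CV 0.4 takes back 0.022 to 0.049.

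**Step 5, how long the lag could be.** Background and Rationale reports 2,551 patients in the institutional database, and Study Duration says that the group "performs five laparoscopic inguinal hernia repairs per week", which it calls conservative. That is 2,551/5 = 510 weeks, or 9.8 years of cases; at ten a week it is 4.9 years. This bears on the controls only if they are drawn from the whole database, which the plan does not say.

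**The case against.** The strongest reply is that every quantity driving the size is assumed. The documents give no charge level, spread, price trend or control year. Mild but reasonable choices leave the error rate near nominal: 2% a year with a 1-year lag, or 3% with CV 1.0, gives about 5-7%. A 1:1 match needs only 140 controls, which is 140/5 = 28 weeks of cases at the stated volume, although matching needs a larger pool. A recent control window therefore fits the text as well as a ten-year one. All of this stands. It limits the claim about size but does not remove the gap, because nothing in the plan keeps the window short.

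Two stronger readings are tempting, and the documents support neither.

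- A reader might infer that the comparison is biased against Sugammadex. That needs rising charges, on which the documents are silent. A trend to shorter stays or fewer admissions would lower current bills and favour Sugammadex.
- A reader might infer from Funding Source, "The budget for the study includes cost of the drug (Sugammadex), pharmacy and IRB fees, and payment for the research team", that the drug is left off the bills and the comparison is invalid. The text available does not say whether the drug is billed, and the budget and consent pages were not available to this review. Even if it is not billed, the total remains valid as charges to patients, which is how Study Objectives and Hypotheses define the outcome. What remains is a point of terminology.

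It is also fair to say that indexing would not make this a strong test. Even with no lag, the largest possible retention effect gives only about a 15% chance of a significant result in favour of Sugammadex (CV 0.4). A 1-year lag at 3-7% cuts that to 1-5%.

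**Conclusion.** The point holds in limited form. Followed exactly, the plan confounds the charges comparison with price year. Rising charges would work against Sugammadex, but the net direction is unknown.

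With 140 per group and no true difference, the false-positive rate is about 5-7% in mild cases (2% a year, 1-year lag, CV 0.4 to 1.0). At CV 0.4 and 3-7% growth it is about 10-30% at 1 year and 47-99% at 3 years. Growth, lag, CV and the log-normal shape are assumptions. A multi-year lag is possible, not established; what is established is that the window is unstated.

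The effect is confined to a secondary outcome, though one that carries its own directional hypothesis. Retention and its sample size are untouched.

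**What to change.** In the statistical section, state the first and last surgery dates for the neostigmine controls. Before the planned rank test, convert every bill to one price year: multiply it by the value of a named index in the reference year divided by its value in the year of surgery. Report the distribution of surgery years in the matched controls.

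This costs a few lines of text, one index and a little analysis work. It needs no extra patients and leaves the matched set and the primary outcome unchanged. There are two limits: an index only approximates this hospital's own price changes, and it does not correct for changes in practice over time. Restricting or matching controls on calendar period would also deal with price year, but it shrinks the control pool and changes the matched set used for retention, so indexing is less disruptive.

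As a minor separate clarification, name the outcome once as billed charges, in place of hospital cost in the statistical section, and state whether the grant-funded Sugammadex appears on the patient's bill.
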